All women who meet the eligibility criteria and are interested in participating in the study will undergo written informed consent, which will be available in English and isiXhosa. The consent form will confirm the eligible woman’s understanding of the study procedures and her informed willingness to participate. The key messages of the informed consent process will include: 1) a description of the study goals and procedures, 2) voluntary participation in the study, 3) confidentiality and privacy with use of the app and study data, 4) the right to withdraw at any time, and 5) the standard of care received at the MOU or any other healthcare facility will not differ according to participation in the study. Specifically, we will request written informed consent for installation of the app, location tracking, data collection, medical record review (participant and infant), one blood draw, and re-contacting by study staff.

Once the consent form has been explained to the participant, any questions she may have will be answered. If the participant agrees to provide consent for participation, she will indicate this with her signature on the consent form. If she does not wish to participate or does not provide her consent for all the activities, she will not sign the consent form and will not be enrolled. A second copy of the form will be provided for her to sign as well and keep. The study staff member who administered the form will provide his or her name, signature and date as a witness to the signing. Signed informed consent forms will be stored in binders within a locked office and only accessible by study staff.

Linkage information and study ID assignment

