Mobility data will be collected throughout the follow-up period. Geospatial coordinates will be recorded with a timestamp. Upon bulk extraction of these data, we will import location information as decimal degree coordinates into ArcMap spatial analysis software. Data charges related to the app are reverse-billed through our app development consultants to ensure timely transmission of data with no cost to participants.

Weekly raffle incentive

To encourage participants to keep the CareConekta app installed on their phone and the GPS function enabled throughout the entire study period, we will offer an incentive: a weekly raffle of one 200MB data bundle (worth approximately \$4). Participants will be eligible to enter the raffle if their phone sent GPS coordinates at least once per day for the prior week. Winners will be randomly selected among all eligible participants using a randomization code automated in STATA. The weekly raffle incentive will only apply to participants enrolled from October 2020 onwards and who have signed version 5.0 or later of the Informed Consent document. There is no limit to the number of times a participant may win the raffle.

Six-month postpartum follow-up visit procedures

Recontacting participant

All participants will be recontacted six months postpartum to return to the study site for a one-time visit. A minimum of three contact attempts by phone and/or home visit will be made for each participant. All contact attempts (successful or not) will be recorded on a contact log.

Follow-up questionnaire

Study staff will complete a face-to-face questionnaire with each participant. This follow-up questionnaire will include reasons for overall acceptability of CareConekta (standard or enhanced), reasons for travel and clinic switching, and barriers and facilitators to care since the start of the study. Response options primarily will be categorical, with open-ended questions to allow for deeper elaboration. Additional questions will be asked of participants in the intervention arm regarding acceptability and feasibility of the intervention. Responses will be recorded directly into a REDCap database by an interviewer using a tablet computer or laptop. This questionnaire may be conducted telephonically.

Viral load testing and potential blood draw

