In routine care in this setting, viral load tests are to be repeated every three months in pregnancy and every six months during breastfeeding, so we expect that most women will have a routine viral load completed before six months postpartum. To avoid additional blood draws for the participant, at the follow-up visit, the study staff will check NHLS to determine the most recent viral load test. If the participant has had no viral load test within 3 months prior to the six-month study follow-up visit, a blood draw for viral load will be conducted by the clinical staff at the Gugulethu CHC. A clinic nurse will collect 5 ml of venous blood, which will be transported daily to the National Health Laboratory Services (NHLs) for HIV viral load testing (Abbott Molecular RealTime HIV-1 assay (Abbott Molecular, Illinois, USA). We will not recontact participants about viral load results unless participants are on ART and the viral load result indicates lack of viral suppression. In that case, results will be made available to participants over the phone (or in person, at participant's wish) with appropriate referrals. For all participants, viral load results will be captured using the participants provincial folder number into the NHLs database, as is standard practice for routine laboratory results in South Africa.

Uninstall app

During the follow-up visit, the CareConekta app will be uninstalled from each participant's phone.

Reimbursement

After all the above steps are complete, the enrollment visit will conclude with providing the participant R150 reimbursement for transport and missed opportunity costs. Payment will be made in cash and/or grocery vouchers and will be recorded in a reimbursement log.

File review activities

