Another risk to participants is that an HIV-positive status may be discerned through disclosure of participation in the study. However, we will do everything possible to minimize the risk of disclosure. We only will communicate with participants outside of the study if they do not return for their follow-up visit. No communication, whether on the phone or by text message, will identify the participant as HIV-positive. Importantly, among participants in the intervention arm who receive notifications of new facilities and phone calls and/or WhatsApp messages, the study staff will not use HIV-specific language. To avoid the possibility of inadvertent disclosure, ART facilities will only be referred to generically as "clinics" and any reference to ART will be to "tablets," a common term for any medication that we demonstrated was acceptable in an earlier mHealth study in South Africa.⁴⁴ We considered providing smartphones to all study participants, but felt that this might lead to inadvertent disclosure of HIV status through one's participation in the study, as well as potential issues related to coercion.

Additionally, discomfort or distress may arise from answering interview questions about behaviors or feelings. We will explain the nature of the questions to be asked during the consent process and all participants will be able to refuse to answer questions or terminate the interview at any time. Women who indicate psychological distress during study visits or interviews will be referred for support and counseling at the MOU. The interviews are designed to be supportive and non-confrontational and attempts will be made during administration of the study to minimize the discomfort of participants. Interviews will be conducted in private rooms with closed doors within the clinic that provide privacy for the participants. If an individual is uncomfortable during an interview, she will be reminded that she can terminate the interview and/or withdraw from the study at any time.

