Risk to subjects will be minimized by: 1) training research staff in the ethical conduct of research; 2) strict protection of confidentiality by detailed standard operating procedures and on-site monitoring; 3) careful handling of sensitive data, procedures and processes in place to ensure data is securely stored and transferred; and 4) referral of participants to appropriate social and health services when necessary. The study site is well connected with the social worker and psychology services at the site as well as local non-governmental organizations providing counselling and support. While the potential risks to subjects are low, any social harm will be reported to the PI and a serious event will be reported to the Vanderbilt University and University of Cape Town IRBs within 48 hours of becoming aware of the event. Should any respondent experience discomfort or distress from participation in the study, we will provide the participant with the appropriate referral needed for follow-up and care.

Risk to subjects from participation in the study is minimal. All possible precautions will be taken to ensure complete confidentiality and protection of study participants. Given the minimal risk, the overall benefit of the study outweighs the risks.

Potential benefits of the proposed research to participants and others

The participants in the intervention arm who receive notifications while traveling may benefit from improved linkage to care while traveling and may have improved HIV-related outcomes. Moreover, the information obtained in this study will provide valuable information for future design and implementation of interventions aiming to improve retention in care among HIV-positive postpartum women. In addition, information obtained from participants will help inform our understanding of mobility among postpartum women and how it may contribute to HIV-positive women dropping out of care after pregnancy.

Data and safety monitoring plan

The study team will undergo extensive training prior to beginning the study, including training on issues of confidentiality. The PI has extensive experience with conducting research studies in South Africa and in training staff in the ethical application of research. In addition, the study team will be trained in ethical conduct of research.

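### A woman off ART whose unsuppressed viral load result arrives after the six-month visit has no committed route to that result or to the referral tied to it

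*Combined protocol and SAP*

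**What the plan says.** The rule is in the protocol under Six-month postpartum follow-up visit procedures, Viral load testing and potential blood draw. Staff look up the most recent test in the National Health Laboratory Services (NHLS) database at the visit. If there was none in the previous 3 months, a sample is taken: "A clinic nurse will collect 5 ml of venous blood", which is then sent to the laboratory. On returning results the section says: "We will not recontact participants about viral load results unless participants are on ART and the viral load result indicates lack of viral suppression". It continues: "In that case, results will be made available to participants over the phone", with in-person return if the woman prefers, and with appropriate referrals. It also says: "For all participants, viral load results will be captured using the participants provincial folder number into the NHLs database".

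Four other places bear on the point:

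- Follow-up questionnaire: the six-month interview covers "barriers and facilitators to care since the start of the study". The Table of schedule of measures adds ART adherence and pharmacy records at six months.
- Informed consent: consent is sought for "medical record review (participant and infant), one blood draw, and re-contacting by study staff", among other items.
- Potential risks of the proposed research to participants and others, on confidentiality: "No communication, whether on the phone or by text message, will identify the participant as HIV-positive". The same paragraph limits communication outside the study to women who miss the follow-up visit.
- The same section, on minimizing risk, lists "referral of participants to appropriate social and health services when necessary".

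**The concern.** The two conditions are joined by *and*, so a woman off ART fails the first whatever her result. The referral goes to women with an unsuppressed result who are on treatment, and not to women with an unsuppressed result who are on none. No reason is given for the ART condition, and the section does not say how being on ART is established (self-report, dispensing record or clinical judgment).

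What is at stake is patient safety. The Introduction presents postpartum loss from HIV care as the problem that motivates the study, and the study reports vertical transmission as an outcome. Being off ART is not the same as being out of care, and the point does not depend on equating them. A woman with detectable virus and no treatment is nonetheless someone for whom a prompt to return to treatment is plainly relevant.

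**Working it through.** No figure is stated or implied, so the check is a reading of the rule against the rest of the protocol.

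**1. Can the case arise?** Yes. The inclusion criteria require HIV-positive status and pregnancy of at least 28 weeks, but not ART use. The study draw depends only on there being no test in the previous 3 months. A woman off ART can therefore be enrolled, attend at six months and be drawn.

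**2. What does the rule do in each case?**

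| ART status | Result | Recontact by the study | Referral tied to the result |
|---|---|---|---|
| On | Unsuppressed | Yes | Yes |
| On | Suppressed | No | No |
| Off | Suppressed | No | No |
| Off | Unsuppressed | No | No |

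Only the last row is in question. The table shows the rule's logic; it does not measure how many women fall in each row or their risk.

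**3. When does the rule bind?** It governs recontact, that is, contact after the visit. A result already on NHLS when staff check can be raised face to face; the protocol neither requires nor forbids this. The firm gap is therefore a result that becomes available after the visit. The main source is the study draw, since that sample has to go to the laboratory.

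**4. Does another provision close the gap?**

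- Entry in NHLS is record-keeping. Nothing says that it leads to the woman being told.
- The nurse who takes the sample does so before the result exists.
- The adherence and barriers questions may reveal at the visit that she is off ART, and she may then be referred. That does not return a later result.
- Pharmacy records are scheduled at six months, but File review activities places file review after the final visit, so they may not inform what is said on the day.
- The general referral wording does not mention viral load results.
- The sentence on communication outside the study narrows contact and adds no route.

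No provision in the protocol commits the study to returning a later unsuppressed result to a woman off ART.

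**5. How many women?** This cannot be derived. It would need the proportions who attend, are off ART, have no test in the previous 3 months, and are unsuppressed. The documents give none of these for this cohort.

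**The case against.** The best case for the rule is that recontact is reserved for the unexpected result, namely viraemia despite treatment. Viraemia off treatment is expected; the actionable fact is that the woman is off ART, and that can be discovered and acted on at the visit. The sample is taken by clinic staff and the result is lodged as a routine result would be, so routine care may pick it up. The consent form may also contain terms on returning results.

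Some of this stands. The visit gives staff a real opportunity to learn that she is off ART and refer her, and routine clinicians may act on the laboratory record. Both are reasons to keep the weight low. The rationale about expected viraemia is plausible, but the documents do not state it. It also does not explain why the referral, as well as the number, should be withheld. The consent form cannot be checked, so the point is confined to the protocol text.

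A reader might infer something stronger: that the study never tells a woman off ART her result, or that she leaves without clinical attention. The documents do not support either. The sentence does not restrict what is said at the visit, a result already on NHLS may be discussed there, and referral in person remains possible.

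**Conclusion.** The point holds as a minor patient-safety improvement. When an unsuppressed result becomes available after the six-month visit, chiefly from the study draw, the protocol commits the study to recontact and referral for a woman on ART, and makes no such commitment for a woman off ART. What she may miss is the later result and the referral tied to it.

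Its size in women is unknown. No sample size, endpoint or analysis changes. The conclusion rests on reading the two conditions as jointly required, which is the plain meaning, and on the consent form not already providing for return of such results. It does not depend on which threshold (≤50 or ≤1000 copies/ml, both used in the analysis plan) defines lack of suppression; the section on viral load testing does not say.

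**What to change.** 1. In Viral load testing and potential blood draw, delete the clause requiring that participants be on ART, so that lack of viral suppression is the only condition for recontact. The existing phone or in-person return, with referrals, then covers every woman with an unsuppressed result. The content of the referral stays with the sponsor and site clinicians.
2. In Potential risks of the proposed research to participants and others, amend the sentence limiting communication outside the study to women who miss the follow-up visit, so that it also permits recontact about viral load results. It already sits awkwardly with the recontact of women on ART.

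If the sponsor prefers to keep the ART condition, the protocol should give the reason and commit to another referral route for women off ART.

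**Cost.** A protocol amendment, with review by the three boards named under Ethical review process, and some extra calls by existing staff through an existing route. The listed consent items already include recontact by study staff. Some women called will already know that they are unsuppressed. More calls add a small risk of disclosing HIV status. The existing rule against identifying a participant as HIV-positive in any phone or text communication addresses this, as does the option of in-person return.

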Electronic and paper files will be reviewed after the participant's final visit to assess engagement in HIV care. If the participant fails to return for a final visit, files will be reviewed a minimum of seven months after estimated delivery. Electronic data on health facility visits and pharmacy dispensing, including facility recorded deaths, will be requested the Provincial Health Data Centre of the Western Cape Department of Health by providing a list of folder numbers of women who have consented and enrolled in the study. These data include all public health facilities in the Western Cape Province, which is the location of the study site. Laboratory records, including viral loads, from any South African facility will be abstracted from the NHLS database. Participants in both arms who are lost from the study at the time of study close will be traced through staff outreach and electronic/paper medical records. Informed consent will include permission to link with electronic medical records.

Table of schedule of measures

Item for completion	Enrolment	Early postpartum phone call	6 months postpartum
Eligibility Checklist	x		
Informed Consent	x		
Linkage form	x	x child details	
Randomisation log	x		
Demographics and medical history	x		x
Maternal mobility (past and planned)	x		x
Maternal clinic switching	x		x
Perceived barriers and facilitators of engagement in care	x		x
Depression (PHQ-4)	x		x
Alcohol and drug use (AUDIT-C and DUDIT Q1)	x		x
Patient provider relationship scale	x		x
ART adherence	x		x
WHO VAW (intimate partner violence)	x		
Social impact scale (stigma)	x		
Availability of social support	x		
Life events (trauma)			x
Infant health			x
Child mobility			x
Acceptability of CareConekta			x
Impact of COVID-19 & lockdown of HIV care and mobility			x
Laboratory tests			
HIV viral load*			x
Record review			
Antenatal and obstetric information	x	x	x
ART pharmacy records	x	x	x
Maternal laboratory results	x	x	x
Child HIV testing		x	x

* If no routine viral load result found in the three months before the study visit

DATA COLLECTION AND STORAGE

Data collection methods

Data will be collected in three ways:

- Face-to-face enrollment and follow-up questionnaires

- Medical record review (electronic and paper file records) to determine participant engagement in HIV care
- Electronic app usage and mobility data

Questionnaire data

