Aim 1a. To use GPS location data from CareConekta and spatial analysis to characterize peripartum mobility within the complete observational cohort (n=200), including the frequency, distance, and timing.

Outcome: Mobility within the study period

We will use data from all 200 participants to describe mobility within a complete observational cohort. In order to assess mobility comprehensively, we will use multiple data sources: time- and date-stamp data as well as geographic location data from CareConekta, participant self-report during questionnaires, and electronic medical records during the file review. Participant questionnaire data and medical record data will be exported from REDCap, and mobility data from CareConekta will be imported from .csv files to SAS for data analysis. To assess the primary outcome of interest, we will report the number of participants who travel during the study period (defined as >50 km for >7 days), over the denominator of all participants. Among those who travel, we will report the median and interquartile range number of trips during the study period and will determine timing and

frequency of travel as it relates to delivery date, which will be obtained from participant questionnaire and/or medical records. Median and interquartile range duration of travel will be reported in days, and we will also assess temporicity (frequency of trips x duration of trips). Reasons for travel will be obtained from the enrollment and follow-up questionnaire and will be grouped by theme, such as family, work, housing, and education.

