Aim 2b. To evaluate the initial efficacy of the enhanced CareConekta intervention, using notifications and staff contact to improve engagement in HIV care, by assessing the association between study arm and engagement in HIV care at six-months postpartum.

Outcome: Efficacy of the intervention

The overall efficacy analysis will include participants in both arms (n=200). To assess overall cohort engagement in HIV care, we will report retention in care, which will be assessed at the six-month postpartum point and defined as no documented HIV-specific contact with any healthcare facility (including medication pick-ups) for >3 months. We also will report viral suppression six months after delivery based on the viral load test closest to the six-month period, using thresholds of ≤50 and ≤1000 copies/ml. Additionally, we will report vertical HIV transmission and completion of the routine 10-week infant PCR test.

Study arm assignment is the primary exposure of interest. We will use Cox proportional hazard regression models to estimate the association of study arm assignment on these outcomes, and will produce adjusted hazard ratios and 95% confidence intervals for retention in care and achieving viral suppression by study arm. We also will identify other predictors of engagement in HIV care. We will produce crude Kaplan-Meier curves to time to loss to follow-up and time to viral suppression by study arm. In a secondary analysis, we will perform an as-treated analysis using self-reported data regarding actually reading the notifications and/or WhatsApp messages or staff phone calls to analyze the effect of receiving the intervention.

HUMAN SUBJECTS' PROTECTION

Ethical review process

The research protocol will be reviewed by the Institutional Review Boards at Vanderbilt University; the University of California, San Francisco; and the University of Cape Town in South Africa. All research activities will occur in South Africa. All procedures will conform to U.S. and South African ethical standards for human subjects' research.

Informed consent

Informed consent will be obtained for all participants as described in the "Informed Consent" section above.

Privacy and confidentiality

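### Retention in Aims 1b and 2b may count as lost some women who continue HIV care outside the Western Cape, and no planned analysis shows how much this matters

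*Combined protocol and SAP*

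**What the plan says.** **Outcome.** The analysis plan for Aims 1b and 2b assesses retention at six months postpartum, "defined as no documented HIV-specific contact with any healthcare facility (including medication pick-ups) for >3 months". As worded this describes loss, and it is read that way here. Any facility counts, in any province.

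**Sources.** File review activities (Study Procedures) requests facility visits and pharmacy dispensing from the Western Cape data centre: "These data include all public health facilities in the Western Cape Province, which is the location of the study site". It adds a national source for laboratory results only: "Laboratory records, including viral loads, from any South African facility will be abstracted from the NHLS database". Women in either arm who are lost from the study at its close "will be traced through staff outreach and electronic/paper medical records". Data collection methods lists "Medical record review (electronic and paper file records) to determine participant engagement in HIV care".

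**Other relevant data.** The six-month questionnaire asks about "reasons for travel and clinic switching, and barriers and facilitators to care since the start of the study" and may be done by telephone. For mobility, Aim 1a combines app data with "participant self-report during questionnaires, and electronic medical records during the file review".

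**Expected travel.** Study Site describes women moving between Cape Town and the Eastern Cape in pregnancy and postpartum. The Introduction says that silent transfers usually go unrecognised because facility data are not linked, and calls this misclassification.

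**Planned extra analyses.** Aim 1b varies the mobility cut-off. Aim 2b adds an as-treated analysis. Neither varies how retention is ascertained.

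**The concern.** The outcome is national, but the data that would show most contacts, namely visits and drug collections, are provincial. A woman who collects her treatment in the Eastern Cape is retained under the definition, yet she may have no such record in the data requested.

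The error is not spread evenly. It falls on women who leave the province, so it is tied to the Aim 1b exposure. It is also tied to the Aim 2b mechanism, because the intervention points women more than 50 km away to facilities near their new location. Care gained that way, when it lies outside the province, is the care least likely to be recorded.

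Sample Size says that the pilot will inform the size of later studies. A larger sample does not remove this error, so a later trial using the same sources would inherit it.

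**Working it through.** **1. The plan's own figure.** Sample Size expects 25% of 200 women to travel long distance: 200 × 0.25 = 50, as stated. With 1:1 allocation, that is about 25 of the 100 control women used in Aim 1b.

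**2. Do the other sources close the gap?**
- *Laboratory records.* Viral load testing and potential blood draw says that routine "viral load tests are to be repeated every three months in pregnancy and every six months during breastfeeding". If tests are evenly timed (assumption), one falls in a given 3-month window with probability 3/6 = 0.5.
- *Tracing.* It covers women lost from the study. A woman who answers the six-month questionnaire by telephone from another province need not be lost from the study, even if no record of her care is found.
- *Questionnaire.* Clinic switching is asked. The plan does not say whether the answers carry dates or count towards retention.

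So the gap is narrowed, not closed.

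**3. Illustration for Aim 1b, assuming no true effect of mobility.** Let L be true loss and m the share of truly retained travellers whose care is not seen. The documents do not give m; it is assumed here to run from 0 to 0.25. L is set at 25.2% and 47.9%, two loss figures from the Introduction.

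Apparent loss in travellers = L + (1 − L)m. Risk ratio (RR) = apparent loss / L. Approximate hazard ratio (HR) = ln(1 − apparent loss) / ln(1 − L). Women miscounted = 25(1 − L)m.

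| L | m | Apparent loss | RR | HR | Women miscounted |
|---|---|---|---|---|---|
| either | 0 | L | 1.00 | 1.00 | 0 |
| 0.252 | 0.05 | 0.289 | 1.15 | 1.18 | 0.9 |
| 0.252 | 0.10 | 0.327 | 1.30 | 1.36 | 1.9 |
| 0.252 | 0.25 | 0.439 | 1.74 | 1.99 | 4.7 |
| 0.479 | 0.05 | 0.505 | 1.05 | 1.08 | 0.7 |
| 0.479 | 0.10 | 0.531 | 1.11 | 1.16 | 1.3 |
| 0.479 | 0.25 | 0.609 | 1.27 | 1.44 | 3.3 |

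A rough guide to m: if viral load were the only recovering source and every test were found, m = 0.5e, where e is the share of retained travellers with all their care in that window outside the province. Then m = 0.05 to 0.25 means e = 10% to 50%.

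**4. Travellers not recognised as such.** A woman who leaves, stops sending location data and misses follow-up may be classed as non-mobile. Let M = 25(1 − L)m be the missed women and s the share of them unrecognised:

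RR = [(25L + M(1 − s)) / (25 − Ms)] / [(75L + Ms) / (75 + Ms)].

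At s = 0.5 and m = 0.05 to 0.25, RR is 1.07 to 1.39 (L = 0.252) or 1.04 to 1.19 (L = 0.479).

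If truly lost travellers also go unrecognised, let A = 25 × apparent loss and p = (A + 75L)/100. RR equals 1 when s = (A − 25p) / [A(1 − p)]. For the same m this is 0.13 to 0.46 (L = 0.252) or 0.07 to 0.33 (L = 0.479). Above that share the sign reverses.

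**5. Sampling error in Aim 1b.** SE(ln RR) = √[(1 − L)/(25L) + (1 − L)/(75L)] = 0.398 and 0.241. The 95% limits around RR = 1 span a factor of exp(1.96 × SE) = 2.18 and 1.60. The largest illustrated bias is ln(1.74)/0.398 = 1.4 or ln(1.27)/0.241 = 1.0 standard errors.

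**6. Aim 2b, both directions.**
- *Hidden benefit.* Assume true loss of 47.9% in control travellers and 25.2% in everyone else. The arm difference is 0.25 × (0.252 − 0.479) = −5.7 points. If a share m is unseen in both arms it becomes −5.7 × (1 − m): −4.5 points at m = 0.20 and −2.8 at m = 0.50. It is 0 if none of the gained care is seen.
- *Apparent harm.* Assume no true effect, but a share r of retained intervention-arm travellers move to unseen out-of-province care because of the messages. Apparent loss in that arm rises by 0.25 × (1 − 0.252) × r: 1.9 points at r = 0.10 and 4.7 at r = 0.25.
- *Sampling error.* √[2L(1 − L)/100] = 6.1 or 7.1 points.

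**The case against.** **The plan has out-of-province sources.** This stands. A reader might infer that care elsewhere is invisible. It is not: national laboratory records, paper files and tracing can all show it, and File review activities already lists them as sources for engagement. Nor does silence on the questionnaire mean that it is excluded. What remains is partial coverage and no analysis of its effect.

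**The number affected may be very small.** This also stands. The Aim 1b exposure is any travel over 50 km, which includes short trips and trips within the province. The Introduction describes circular migration. To be miscounted, a woman must have all her recorded contact elsewhere for more than 3 months. The documents do not say what share of travel leaves the province, so m could be near zero.

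**The loss rates are not true loss.** Correct. They are recorded loss to follow-up, which by the Introduction's own account may include silent transfers, and 25.2% is a one-year figure. A lower true rate would raise the ratios, so the table is not a bracket.

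**Viral suppression is safe because laboratory data are national.** A reader might infer this, but the protocol captures results through the provincial folder number and places the fallback draw at the Gugulethu site. How well tests done elsewhere are found is not stated.

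**It is a small pilot.** This lowers the severity. It does not remove the point, because the estimates are meant to guide later studies.

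**Conclusion.** The point holds as a limited one: followed as written, the plan can misclassify retention in a way tied to mobility, and nothing planned would show by how much.

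Two stronger readings are not supported. One is that Aim 1b must exaggerate the harm of mobility. That is the tendency among women recognised as travellers, but unrecognised travel can shrink or reverse it. The other is that Aim 2b must be biased towards no effect. It can hide benefit, but it can pass the null and suggest harm if messages move care from Cape Town to clinics in other provinces.

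The size cannot be derived from the documents. The figures above rest on assumed m, s and r, on a 25 to 75 split taken from an undefined long-distance travel figure, and on borrowed loss rates. Under those assumptions the Aim 1b bias is at most 1.4 standard errors, and the Aim 2b shifts are smaller than one standard error of the arm difference. Severity is minor to moderate.

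**What to change.** 1. Keep the primary retention outcome record-based. State that all sources in File review activities count, and that they are searched and applied identically in both arms. This mostly confirms the present plan.
2. Add a sensitivity analysis of Aims 1b and 2b, by arm and by mobility group. Take women with no contact found and app or questionnaire evidence of being outside the province. Count them first all as lost, then all as retained. The inter-provincial measures planned under Aim 1a can help to identify them.
3. Where the six-month questionnaire or tracing does record out-of-province care, also report retention with that care counted, as a secondary result only. Do not use the intervention-arm call logs, which have no control-arm counterpart.

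**Cost.** Items 1 and 2 need a paragraph of analysis-plan wording and a table, using data already collected. Bounds will be wide in a sample this small. Item 3 is weaker: the protocol does not say that tracing records reported care or that the questionnaire dates it, and a rule of more than 3 months needs dates. Self-report may also differ by arm, because only intervention-arm travellers are contacted about their medication supply.
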